5.6 Health economic endpoints (UK only)

- Mean cost from the perspective of NHS at 180 days post-randomisation
- Quality Adjusted Life Years (QALY) at 180 days post-randomisation
- Incremental cost-effectiveness ratio

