The estimation of a confidence interval for the ICER statistic can be problematic for the following reasons: i) differences in QALYs between treatment arms tend to be very small, meaning that the denominator in the ratio may be zero or very close to zero, leading to an undefined value for the ICER; ii) high levels of skew due to a tendency for outliers and zero values in patient-level cost data; iii) costs and outcomes cannot be assumed to be uncorrelated. Non-parametric bootstrapping with replacement based on the observed data is an accepted approach to estimating confidence intervals for the ICER (22). The bootstrapping process will be carried out with 5000 iterations based on the original cost and outcome data using Stata/IC to achieve stability for interval estimates. Regression models will adjust for covariate imbalances on each bootstrapped re-sample. Adjusted incremental cost and outcome estimates will then be used to construct the mean and 95% confidence interval for the ICER. The distribution of incremental estimates will be plotted on a cost-effectiveness plane. A cost-effectiveness acceptability curve (CEAC) will plot the probability of cost-effectiveness of the intervention as a function of willingness-to-pay values per additional QALY gained in order to place the intervention in the context of

current acceptable willingness-to-pay levels for new healthcare technology according to the National Institute for Health and Care Excellence (NICE) (23).

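### Section 8.3 fixes a bootstrap mean and 95% interval for the ICER although the QALY difference may be near zero; resampling does not cure that, and an interval of ordered ratios would then have no decision meaning

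*Protocol*

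**What the plan says.** Section 5.6 of the protocol lists "Incremental cost-effectiveness ratio" as the third of three UK-only health economic endpoints, after mean cost and QALYs at 180 days.

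Section 8.3 gives three reasons why an interval for the ICER is difficult: a very small QALY difference, skewed costs, and correlation between costs and outcomes. On the first it says that "the denominator in the ratio may be zero or very close to zero, leading to an undefined value for the ICER". It then presents non-parametric resampling as an established answer: "The bootstrapping process will be carried out with 5000 iterations based on the original cost and outcome data using Stata/IC", with the regression adjustment repeated in each resample. The output is stated as: "Adjusted incremental cost and outcome estimates will then be used to construct the mean and 95% confidence interval for the ICER".

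Two displays follow: "The distribution of incremental estimates will be plotted on a cost-effectiveness plane", and "A cost-effectiveness acceptability curve (CEAC) will plot the probability of cost-effectiveness of the intervention as a function of willingness-to-pay values".

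The section does not name the type of bootstrap interval. It does not say whether the mean is the average of the replicate ratios or the ratio of the mean increments. It gives no rule for replicates in different quadrants and plans no interval on the net-benefit scale.

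**The concern.** The bootstrap deals with two of the three listed difficulties, skew and correlation. It does not deal with the first, since each replicate is again a ratio over a QALY difference that may be near zero. Two consequences follow when the replicates straddle zero.

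- **Interval.** A negative ratio arises both when the intervention is cheaper and better (dominant) and when it is dearer and worse (dominated). Positive ratios likewise mix dearer-and-better with cheaper-and-worse. Sorting the ratios and cutting off the tails places opposite conclusions side by side, so the limits do not bound anything a decision-maker can use.
- **Mean.** If the mean is taken as the average of replicate ratios, it has no finite value to settle to, because the denominator has density at zero. More iterations do not help.

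At stake is the reported ICER and its uncertainty, which is a listed endpoint.

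**Working it through.** **Plan's own figure.** There is none to reproduce. The protocol gives no cost, QALY or ICER value, and no number of UK patients.

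**Inputs from the protocol:** 5000 iterations; a ratio of adjusted increments; a denominator that may be near zero (all section 8.3). The figure of 1251 per arm (section 8.1) serves only as an upper bound for the UK subset.

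**Assumed inputs, not in the documents:** SD of 180-day QALY 0.12; SD of cost 9,000 pounds; correlation of the increments -0.2; 600 per arm; QALY gain 0 to 0.028; extra cost 300 pounds (a saving of 400 pounds as a variant); willingness to pay 20,000 pounds per QALY.

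**Step 1: standard errors.** SE = SD × √(2/n).
- QALY: 0.12 × √(2/600) = 0.00693
- Cost: 9,000 × √(2/600) = 520 pounds

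A gain of 0.007 is therefore 0.007/0.00693 = 1.01 SE.

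**Step 2: share of replicates with a QALY difference at or below zero.** This is Φ(-z), where z is the gain in SE units: 50% at z = 0, 31% at 0.5, 16% at 1, 2.3% at 2, and 0.1% at 3. Straddling is thus material up to roughly 2 to 3 SE.

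**Step 3: simulated replicates.** Bivariate normal draws stand in for 5000 bootstrap pairs, repeated with 20 seeds; extra cost 300 pounds, 600 per arm. Ranges are over the 20 seeds. Percentile limits are averages over the seeds. Quadrant shares are from one run.

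| Gain (SE units) | Average of ratios, range | Ratio of mean increments, range | 2.5% and 97.5% limits | Dominant | Dominated |
|---|---|---|---|---|---|
| 0 (0) | -213,095 to 465,538 | -191,865,347 to 44,174,083 | -1,111,528 to 1,055,187 | 16.9% | 39.2% |
| 0.003 (0.43) | -2,354,379 to 3,160,605 | 90,904 to 110,524 | -1,035,578 to 987,686 | 20.9% | 26.8% |
| 0.007 (1.01) | -5,605,245 to 608,183 | 40,141 to 45,844 | -689,622 to 777,618 | 25.6% | 12.7% |
| 0.014 (2.02) | -464,165 to 97,965 | 20,078 to 22,649 | -91,158 to 269,126 | 28.1% | 1.9% |
| 0.028 (4.04) | 11,837 to 13,232 | 10,013 to 11,257 | -25,224 to 62,567 | 28.4% | 0.0% |

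In the last row a negative limit can be read, because every negative ratio is a dominant replicate. In the rows above it cannot, or only approximately at 2 SE.

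**Step 4: other assumptions.**
- Saving of 400 pounds, gain 0.007, 600 per arm: limits -706,876 to 605,295, with 67.2% dominant and 5.0% dominated.
- Extra cost 300 pounds, 1251 per arm, gain 0.007 (1.46 SE): limits -432,791 to 578,593, with 19.3% and 6.0%.
- Extra cost 300 pounds, 1251 per arm, gain 0.014 (2.92 SE): limits -29,531 to 127,686, with 20.1% and 0.1%.

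**Step 5: the same information as net benefit.** Incremental net monetary benefit = λ × ΔQALY - Δcost, with λ = 20,000, gain 0.007 and extra cost 300.
- Estimate: 20,000 × 0.007 - 300 = -160 pounds
- Variance: (20,000 × 0.00693)² + 520² + 2 × 0.2 × (20,000 × 0.00693) × 520 ≈ 318,000, so SE ≈ 564
- 95% interval: -160 ± 1.96 × 564, about -1,265 to 945 pounds

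This is defined whatever the QALY difference, and larger is always better.

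**The case against.** **The wording does not say that ratios are averaged.** A reader might infer that the reported ICER would change with the random seed. The documents do not support that as a general claim. The sentence speaks of using incremental estimates to construct the mean, which fits the ratio of mean increments at least as well, and that ratio is steady across seeds unless the QALY difference is about zero. What stands is that the text leaves this open.

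**No interval type is named.** This is correct. The limits above assume a percentile interval. But the target is fixed as a bootstrap interval for the ratio itself, and any method that orders the ratios without regard to quadrant has the same defect.

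**Detail belongs in a later plan.** Section 8.4 promises a prospective analysis plan for secondary studies, including the economic analysis, and section 8.3 leaves missing-data strategy to a health economic analysis plan. Those are natural places for the correction. Neither withdraws what section 8.3 already fixes: the statistic, the resampling method and the number of iterations.

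**The plane and the acceptability curve are planned.** This objection carries the most weight. The plane separates the quadrants, and the curve gives the share of replicates with positive net benefit at each willingness-to-pay value. A reader might infer that the whole economic evaluation would be uninterpretable; it would not.

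**Conclusion.** The point holds for the ICER mean and its interval, and no further. If the QALY gain lies within roughly 2 to 3 SE of zero, a bootstrap interval of ordered ratios mixes opposite conclusions and has no decision meaning. At 1 SE, under the stated assumptions, it runs from about -690,000 to +778,000 pounds per QALY and pools 26% dominant with 13% dominated replicates. At 2 SE the mixing is small (28% and 2%), but the limits remain wide at about -91,000 to +269,000. At 4 SE essentially no replicate is dominated and even the average of ratios is stable.

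The instability of the mean depends on reading it as the average of replicate ratios, which the text permits but does not state.

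The size rests on assumed SDs, correlation, cost difference and UK numbers. The protocol supplies none of these. It does say that QALY differences tend to be very small, which makes the unfavourable range plausible without proving it. The primary and other clinical outcomes are unaffected. This should be corrected before the economic analysis, but it does not threaten the trial.

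**What to change.** In section 8.3, and in the health economic analysis plan:

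1. State that the ICER point estimate is the adjusted mean incremental cost divided by the adjusted mean incremental QALY, not the average of replicate ratios.
2. Replace the 95% interval for the ICER with a 95% interval for incremental net monetary benefit at the willingness-to-pay values used for the acceptability curve, from the same 5000 replicates.
3. Give an ICER interval only if essentially all replicates have the same sign of QALY difference. Otherwise report the quadrant shares beside the plane.

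The cost is two or three sentences. No new data, resampling or patients are needed, since the replicates and the willingness-to-pay values are already required for the planned displays.

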8.4 Secondary studies

The OPTIMISE II trial data will be used for secondary studies directly relevant to the core trial objective including the health economic analysis. A prospective statistical analysis plan will be prepared for each secondary study prior to data analysis.

9. RESEARCH ETHICS

The PI will ensure that this trial is conducted in accordance with the Principles of the Declaration of Helsinki as amended in Tokyo (1975), Venice (1983), Hong Kong (1989), South Africa (1996), Edinburgh (2000), Washington DC (2002), Tokyo (2004), Seoul (2008) and Fortaleza (2013) as described at the following internet site: http://www.wma.net/en/30publications/10policies/b3/index.html. The trial will fully adhere to the principles outlined in the Guidelines for Good Clinical Practice ICH Tripartite Guideline (January 1997). The study will be carried out in accordance with the ethical principles in the Research Governance Framework for Health and Social Care, Second Edition, 2005 and its subsequent amendments as applicable and applicable legal and regulatory requirements. At sites, all accompanying material given to a potential participant will have undergone an independent Research Ethics Committee review within that country. Full approval by the Research Ethics Committee will be obtained prior to starting the trial and fully documented by letter to the Chief Investigator naming the trial site, local PI (who may also be the Chief Investigator) and the date on which the ethics committee deemed the trial as permissible at that site. All members of the trial steering committee will declare conflicts of interest before joining the study group. These will be listed on any publications arising from the trial.

10. DATA HANDLING AND RECORD KEEPING

10.1 Confidentiality

Information related to participants will be kept confidential and managed in accordance with the Data Protection Act (UK), NHS Caldecott Principles (UK), The Research Governance Framework for Health and Social Care (UK), and the conditions of Research Ethics Committee Approval, or corresponding legislation or approvals for a particular participating country or site. The patient's full name, date of birth, hospital number and NHS number (UK) will be collected to allow tracing through national records. The personal data recorded on all documents will be

regarded as confidential. All patient related trial documents are confidential and must be stored securely at each hospital (e.g. patients' written consent forms). The PI must ensure the patient's confidentiality is maintained at all times. The Sponsor will ensure that all participating partner organisations will maintain the confidentiality of all subject data and will not reproduce or disclose any information by which subjects could be identified, other than reporting of serious adverse events. Representatives of the trial management team will require access to patient notes for quality assurance purposes and source data verification, but patients' confidentiality will be respected at all times. In the case of special problems and/or competent authority queries, it is also necessary to have access to the complete trial records, provided that patient confidentiality is protected.

10.2 Data storage

Data will be transcribed on to the paper CRF prior to entry on to the secure OPTIMISE II data entry web portal. Submitted data will be reviewed for completeness and consistency by authorised users within the study group. Submitted data will be stored securely against unauthorised manipulation and accidental loss. Only authorised users at site, or at Queen Mary University of London (sponsor and host of data entry portal) will have access. Desktop security is maintained through user names and passwords. Data back-up procedures are in place. Storage and handling of confidential trial data and documents will be in accordance with the Data Protection Act 1998 (UK).

10.3 Archiving

All trial documentation and data will be archived centrally by the Sponsor in a purpose designed archive facility for twenty years in accordance with regulatory requirements. Access to these archives will be restricted to authorised personnel. Electronic data sets will be stored indefinitely.

10.4 Patient identifiable data

For each participant a unique participant ID and patient initials will be recorded.

UK only: To facilitate linkage to UK national databases for the collection of follow-up data, patient identifiable data will be collected and entered on to the secure data entry web portal. Data will be stored and handled in accordance with the Data Protection Act 1998 (UK). In the event that patient identifiable data needs to be transferred between authorised users, this will occur by email [contact] to

@nhs.net accounts in the UK or equivalent secure email transfer in other countries.

Outside of the UK

No identifiable data is required for the analysis of patients outside of the UK. Data will be stored and handled in accordance with the appropriate data protection legislation for each particular country or site.

11. PRODUCTS, DEVICES AND TECHNIQUES

11.1 Cardiac output-guided haemodynamic therapy

Cardiac output monitors are routinely used in secondary care. For this study, all sites will only use the cardiac output monitoring equipment provided by Edwards Lifesciences. The device comprises of an EV1000 (monitor), ClearSight (non-invasive sensor) and FloTrac (invasive sensor) and clinicians will be able to choose between the two sensors on a patient by patient basis. Please see the Management of Intervention Group SOP for specific details of the intervention.

12. SAFETY REPORTING

12.1 Adverse Events (AE)

An AE is any untoward medical occurrence in a subject to whom an intervention has been administered, including occurrences which are not necessarily caused by or related to that intervention. An AE can therefore be any unfavourable and unintended sign, symptom or disease temporarily associated with study activities. However, OPTIMISE II is a non-CTIMP trial, and all trial interventions are already in routine clinical use for patients undergoing major gastrointestinal surgery. The safety of the intervention will be monitored by recording acute cardiac events at 24 hours and 30 days after randomisation as a trial outcome. These events will be monitored at intervals by the DMEC and will not be recorded separately as an AE on the CRF.

12.2 Serious Adverse Event (SAE)

A serious adverse event (SAE) is defined as an untoward occurrence that:

- (a) results in death;
- (b) is life-threatening;
- (c) requires hospitalisation or prolongation of existing hospitalisation significantly beyond normal inpatient stay for the surgery concerned;
- (d) results in persistent or significant disability or incapacity;

An SAE occurring to a research participant should be reported to the sponsor where in the opinion of the Chief Investigator the event was:

- Related that is, it resulted from administration of any of the research procedures, and
- Unexpected that is, the type of event is not listed in the protocol as an expected occurrence.

OPTIMISE II is an investigation of a perioperative intervention. It is expected that patients undergoing major abdominal surgery will suffer medical complications, with consequences up to and including death. Only complications considered by the CI to be *related to the use of study procedures* and not a typical complication of abdominal surgery should be reported as SAEs.

12.3 Notification and reporting of Serious Adverse Events

Serious Adverse Event (SAEs) that are considered to be 'related' and 'unexpected' are to be reported to the sponsor and the sponsor's representative for that country within 72 hours of learning of the event.

12.4 Reporting a Serious Adverse Event

Individual sites will notify the co-ordinating centre in that country of an SAE by emailing a scanned copy of the supplementary SAE report form to the national coordinator. SAEs will be reported within 72 hours and will be forwarded to the sponsor via the UK co-ordinating centre.

12.5 Urgent safety measures

The CI may take urgent safety measures to ensure the safety and protection of trial participants from any immediate hazard to their health and safety. The measures should be taken immediately. In this instance, the approval of the REC prior to implementing these safety measures is not required. However, it is the responsibility of the CI to inform the sponsor and Research Ethics Committee of this event within three days. The sponsor must be sent a copy of the correspondence with regards to this matter.

12.6 Annual safety reporting

The CI will send the annual progress report to the UK REC and sponsor. For participating sites outside the UK, reports will be submitted as required by the respective national coordinators, with the support of the trial management group.

12.7 Overview of the safety reporting responsibilities

The CI has the overall oversight responsibility. The CI will ensure that safety monitoring and reporting is conducted in accordance with the sponsor's requirements.

13. MONITORING & AUDITING

The Sponsor will have oversight of the trial conduct at each site. The trial team will take day-to-day responsibility for ensuring compliance with the requirements of GCP in terms of quality control and quality assurance of the data collected as well as safety reporting. The OPTIMISE II Trial Management Group will communicate closely with individual sites and the Sponsor's representatives to ensure these processes are effective. A Data Monitoring and Ethics Committee (DMEC) will be appointed (see section 14.3). The PCTU quality assurance manager will conduct a study risk assessment in collaboration with the CI. Based on the risk assessment, an appropriate study monitoring and auditing plan will be produced according to PCTU SOPs. Any changes to the monitoring plan must be agreed by the PCTU QA manager and CI.

13.1 Monitoring the safety and wellbeing of trial participants

The Research and Development departments at each trial site should perform regular audits of research practice. Systems are in place to ensure that all PIs and designees are able to demonstrate that they are qualified by education, training or experience to fulfill their roles and that procedures are in place that assures the quality of every aspect of the trial. The intervention will last less than 12 hours in most cases, therefore it is extremely unlikely that new safety information will arise during the intervention period. Nonetheless should this situation arise, participants will be informed and asked if they wish to discontinue the intervention. If the subjects wish to continue in the trial they will be formally asked to sign a revised approved patient information sheet and consent form. Early termination of trial in response to safety issues will be addressed via the DMEC. Day to day management and monitoring of individual sites will be undertaken via the Trial Management Group composed of the Chief Investigator and supporting staff. They will meet on a regular basis to discuss trial issues.

13.2 Monitoring the safety of investigators

Each site has health and safety policies for employees. All personnel should ensure

that they adhere to health and safety regulations relating to their area of work. The PI will ensure that all personnel have been trained appropriately to undertake their specific tasks. The trial team will complete GCP and consent training prior to start up.

14. TRIAL MANAGEMENT & COMMITTEES

14.1 Trial management group

Day-to-day trial management will be co-ordinated by a trial management group consisting of the Chief Investigator, his/her support staff and members of the PCTU.

14.2 Trial steering committee

The Trial Steering Committee will oversee the trial and will consist of several independent clinicians and trialists, lay representation, co-investigators, and an independent Chair.

Meetings will be held at regular intervals determined by need but not less than once a year. The TSC will take responsibility for:

- approving the final trial protocol;
- major decisions such as a need to change the protocol for any reason;
- monitoring and supervising the progress of the trial;
- reviewing relevant information from other sources;
- considering recommendations from the DMEC and
- informing and advising on all aspects of the trial

14.3 Data monitoring and ethics committee

The Data Monitoring and Ethics Committee (DMEC) is independent of the trial team and comprises of two clinicians with experience in undertaking clinical trials and a statistician. The committee will agree conduct and remit, which will include the early termination process. During the period of recruitment into the trial the DMEC will monitor safety data and routinely meet to assess safety analyses. The trial will be terminated early if there is evidence of harm in the intervention group or if recruitment is futile. The DMEC functions primarily as a check for safety by reviewing adverse events.

15. FINANCE AND FUNDING

The OPTIMISE II trial will be funded by Edwards Lifesciences and the National Institute for Health Research (UK).

16. SPONSORSHIP & INDEMNITY

Queen Mary University of London will act as trial sponsor and provide no fault insurance.

17. PUBLICATION

Data arising from this research will be made available to the scientific community in a timely and responsible manner. A detailed scientific report will be submitted to a widely accessible scientific journal on behalf of the OPTIMISE II Trial Group. The TSC will agree the membership of a writing committee, which will take primary responsibility for final data analysis and writing of the scientific report. All members of the writing committee will comply with internationally agreed requirements for authorship and will approve the final manuscript prior to submission. Please see OPTIMISE II trial publication charter for further details.

pt∧m∧se∏

